### ***2.1.3.3 Other efficacy endpoints***

- First occurrence of CV death, HHF, or urgent visit for HF
- First occurrence of CV death or HHF
- Total occurrences (first and potentially subsequent) of HHF after randomization
- Total occurrences (first and potentially subsequent) of urgent HF visits after randomization
- First occurrence of CV death, HHF, urgent visit for HF, non-fatal myocardial infarction, and non-fatal stroke
- First occurrence of fatal and non-fatal MI
- First occurrence of fatal and non-fatal stroke
- First occurrence of new onset of atrial fibrillation or atrial flutter (adverse events (AEs) with a preferred terms (PTs) of atrial fibrillation or atrial flutter)
- First occurrence of a composite renal endpoint, consisting of events sustained  $\geq 50\%$  decrease in eGFR from baseline (for  $\geq 30$  days), chronic dialysis, renal transplant, or sustained eGFR  $< 15$  mL/min/1.73m^2 (for  $\geq 30$  days)
- First occurrence of severe hypoglycemia
- Total occurrences of the following hypoglycemia categories
  - Severe hypoglycemia
  - Hypoglycemia with documented glucose value  $< 54$  mg/dL
  - Hypoglycemia with documented glucose value  $< 70$  mg/dL
- Days alive and out of hospital (DAOH) and percent DAOH (PDAOH)

- Changes from baseline in NT-proBNP, hematocrit, HbA1c, body weight, and SBP

All time-to-event endpoints are assessed based on investigator-reported events.

Cardiovascular death includes death of undetermined cause.

The first occurrence of the composite renal endpoint is defined as follows:

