### **9.1.2.1 Estimated glomerular filtration rate and dialysis**

Serum creatinine will be assessed as part of serum clinical chemistry at all on-site visits by central laboratory. Estimated glomerular filtration rate will be calculated by the central laboratory using the MDRD equation. The Baseline eGFR value for each patient is defined as the value assessed by the central laboratory at Randomization.

Patients with a suspected renal event (reduction of eGFR) should have a repeat assessment of renal function 30 to 45 days following the onset of the event to confirm it is sustained (this repeat renal assessment may occur beyond the last planned visit per protocol). If acute renal failure is suspected, further clinical evaluation should be performed as per local standard of care, including confirmation of renal laboratory parameters, and consideration should be given to a nephrology referral (see [Appendix E](#)).

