### **10.3.3 List of criteria for permanent treatment discontinuation**

The patients may withdraw from treatment with the IMP if they decide to do so, at any time and irrespective of the reason, or this may be the Investigator's decision. All efforts should be made to document the reason(s) for treatment discontinuation and this should be documented in the e-CRF.

Patients who report a CV or renal endpoint as described in [Section 10.4.1.4](#) should remain on IMP until the end of the study, unless there is a safety concern.

The following reasons shall lead to permanent IMP discontinuation:

- At the patient's own request (ie, withdrawal of consent for treatment) (note that this is regardless of whether or not the patient continues in the study)
- If, in the Investigator's opinion, continuation with the administration of the study treatment would be detrimental to the patient's well-being
- Pregnancy (in female patients)
- Any code breaking requested by the Investigator
- Specific request of the Sponsor
- Patient requires dialysis or renal transplantation

- Estimated glomerular filtration  $<15 \text{ mL/min/1.73 m}^2$

**Note:** the central laboratory will alert the Investigator for eGFR values  $<15 \text{ mL/min/1.73 m}^2$ . A repeat determination should be performed within 2 weeks, and study treatment discontinued if the repeat eGFR is  $<15 \text{ mL/min/1.73 m}^2$  (unless a reversible cause is identified [eg, short-term illness or transient volume depletion], in which case an additional repeat determination can be performed after resolution of the short-term illness).

Any abnormal laboratory value or ECG parameter will be immediately rechecked for confirmation before making a decision of permanent discontinuation of the IMP for the concerned patient.

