#### **13.4 USE AND COMPLETION OF CASE REPORT FORMS (CRFS) AND ADDITIONAL REQUEST**

It is the responsibility of the Investigator to maintain adequate and accurate e-CRFs (according to the technology used) designed by the Sponsor to record (according to Sponsor instructions) all observations and other data pertinent to the clinical investigation in a timely manner. All e-CRFs should be completed in their entirety in a neat, legible manner to ensure accurate interpretation of data.

Should a correction be made, the corrected information will be entered in the e-CRF overwriting the initial information. An audit trail allows identifying the modification.

Data are available within the system to the Sponsor as soon as they are entered in the e-CRF.

The computerized handling of the data by the Sponsor may generate additional requests (DRF) to which the Investigator is obliged to respond by confirming or modifying the data questioned. The requests with their responses will be managed through the e-CRF.

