**2.1.3 Efficacy endpoints**

Efficacy endpoint events with onset date prior to randomization will not be included in efficacy analysis and instead will be treated as pre-treatment adverse events.

In the analyses of time-to-event efficacy endpoints:

- Deaths not included among the events in the endpoint will be treated as competing events;
- Patients alive at the end of the study will be right censored on the date they were last known to be alive;
- Event types and dates included in the analyses will be those as reported by the investigators; and
- In the case where the exact date of occurrence of an event is not known (the day, month, and/or year are missing), the date will be imputed as described in Appendix .

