**Endpoint definitions of renal events for renal endpoint analysis**

Event	Endpoint definition
Sustained <math>\geq 50\%</math> decrease in eGFR from baseline	Confirmed <math>\geq 50\%</math> decrease in eGFR for <math>\geq 30</math> days OR with no repeat eGFR <math>\geq 30</math> days as recorded in eCRF “eGFR decrease”
Sustained eGFR $< 15$ mL/min/1.73 m 	Confirmed eGFR $< 15$ mL/min/1.73 m  for $\geq 30$ days OR with no repeat eGFR $\geq 30$ days as recorded in eCRF “eGFR decrease”
Chronic dialysis	Dialysis lasted for $\geq 90$ days (e.g. end date – start date+ 1 $\geq 90$ ) as recorded in eCRF “Renal Event – Dialysis”, or answered Yes to the question “Does the subject meet the criteria for ESRD”.
Renal transplant Reference source not found.	“Renal transplant” captured in eCRF “Other procedure form”. PTs of Renal transplant, Renal and pancreas transplant, Renal and liver transplant based on MedDRA v23.0.

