**d. Specific censoring rule for composite renal endpoints**

Patients without the event will be considered censored at their earlier of last laboratory sample date where eGFR results are available. If a patient doesn't have the eGFR measurements after a certain timepoint, but a dialysis procedure not meeting the definition of chronic occurs after the last eGFR measurement but before the patient's last study visit date, the patient will be censored at the last start date of dialysis.

Patients who already fulfil the respective condition at baseline or without post-baseline laboratory measurements will be censored at Day 1.

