### Appendix D Key Changes to Original Planned Analysis and Protocol

Change	Rationale
Primary endpoint analyzes total occurrences (first and potentially subsequent) rather than first occurrence	Total occurrences are expected to be a more sensitive indicator of treatment benefit, are clinically relevant to patients with heart failure, and have been sensitive to change in several cardiovascular outcomes trials
Primary endpoint adds urgent HF visit to original planned endpoint of CV mortality and HHF	Urgent HF visits are clinically relevant and can be reduced by effective treatment
All event endpoints based on investigator reporting rather than adjudication	Adjudication was not completed, and investigator-reported events are clinically relevant
Only one primary objective is applied to the overall population: initially there were co-primary objectives, one to demonstrate reductions in CV morbidity and mortality in those with LVEF<50%, and one to demonstrate reductions in CV morbidity and mortality in the overall population	Primary focus is on overall population rather than subgroups
Composite renal endpoint was moved from a secondary objective to other objective; change in eGFR over time was added as a secondary benefit	Given the current follow-up in SOLOIST, change in eGFR over time is a more sensitive measure of renal benefit than the composite renal endpoint
Addition of ARR, DAOH and PDAOH as other endpoints	ARR provides a perspective of treatment benefit, and DAOH and PDAOH capture clinical relevance of decreased hospitalizations
Hypoglycemia safety moved to efficacy endpoint	Reductions in hypoglycemia have been seen with sotagliflozin in both type 1 diabetes and T2D, indicating the value of statistical analyses of hypoglycemia results
CV death and HHF in patients with LVEF <50%, with and without T2D (a secondary endpoint in Amendment 2) is not included in current analysis plan	Limited enrollment after Amendment 2 means subgroup analysis of those without T2D is not adequately powered for a secondary endpoint
All-cause mortality was a secondary endpoint in the original protocol, moved to “other	Original move to “other endpoint” was based on FDA feedback that it would not be included

endpoint” in Protocol Amendment 2, and returned to a secondary endpoint in this analysis plan	in labeling, but it was returned to secondary endpoint because of its high clinical relevance

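### As most naturally read, the SAP takes the renal composite's eGFR events from an investigator-completed form but time at risk from laboratory samples, so a gradual sustained fall of 50% or more in the central data can be censored as event-free

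*SAP*

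**What the plan says.** **Source of events.** SAP 2.1.3 sets the general rule for time-to-event efficacy endpoints: "Event types and dates included in the analyses will be those as reported by the investigators". SAP 2.1.3.3 repeats it directly before the renal definition: "All time-to-event endpoints are assessed based on investigator-reported events". The renal definition table then describes both eGFR components (fall of at least 50% from baseline; eGFR below 15) as either confirmed for at least 30 days or lacking a repeat value at 30 days or more, "as recorded in eCRF “eGFR decrease". SAP Appendix D lists the change from the protocol: "All event endpoints based on investigator reporting rather than adjudication". Its stated reason is that adjudication was not completed. Protocol 13.4 says who fills in the form: "It is the responsibility of the Investigator to maintain adequate and accurate e-CRFs".

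**Source of time at risk.** SAP Appendix A, rule d: "Patients without the event will be considered censored at their earlier of last laboratory sample date where eGFR results are available".

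**The laboratory series.** Protocol 9.1.2.1: "Serum creatinine will be assessed as part of serum clinical chemistry at all on-site visits by central laboratory". The same section has the central laboratory compute eGFR by the MDRD equation. SAP 2.1.1 takes baseline eGFR as the central value at randomization.

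**Prompts to sites.** Protocol 10.3.3 notes that "the central laboratory will alert the Investigator for eGFR values" below 15. Protocol 10.4.6 and Appendix E ask for follow-up of a rapid change of more than 30% against the mean of the two preceding study visits. Protocol 9.1.2.1 asks for a repeat at 30 to 45 days once a renal event is suspected.

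**The concern.** Two of the four components are thresholds on a laboratory value. Sampling, equation and baseline are all central, and applying the threshold needs neither clinical judgement nor adjudication. Yet on the natural reading the event exists only if a site notices the fall and completes a form. No section derives these components from the central series or reconciles the form against it.

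The SAP does use the laboratory series for the other half of the analysis, the censoring date. A patient whose central values show a sustained fall but who has no form therefore contributes event-free follow-up through the period of the fall. Lost events cost precision. If forms are completed at different rates in the two arms, the hazard ratio for these components is also distorted.

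**Working it through.** The documents give no event target, power or form-completion rate for the renal composite, so there is no planned figure to reproduce. The check traces the rules through the visit schedule and then bounds the effect under stated assumptions.

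**1. Which limb does the form govern?** The table allows two readings.
- The form governs both limbs. SAP 2.1.3, 2.1.3.3 and Appendix D all support this.
- The form governs only the no-repeat limb. The source for the confirmed limb is then unstated.

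The first is the more natural. On neither reading does the SAP state a laboratory derivation.

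**2. Can scheduled samples alone settle the 30-day requirement?** Visit days and windows are from Protocol 1.2.
- Day 29 (±3) to Day 113 (±7): 113 − 29 = 84 days; at least 84 − 3 − 7 = 74.
- Later visits, every 4 months (±7), taking a month as 30.44 days: Days 113, 245, 366 and 488, so gaps of 132, 121 and 122 days. The shortest is at least 121 − 14 = 107.

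From Week 4 on, two consecutive qualifying central values always span more than 30 days, with no extra visit.

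**3. Do the prompts catch every such fall?** Take an invented patient with 60 at Days 1, 8 and 15, then a gradual decline. The 30% prompt uses (mean of prior two − current) / mean of prior two.

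| Day | eGFR | Mean of prior two | Below that mean | Below baseline |
|---|---|---|---|---|
| 29 | 50 | 60 | 16.7% | 16.7% |
| 113 | 42 | 55 | 23.6% | 30.0% |
| 245 | 35 | 46 | 23.9% | 41.7% |
| 366 | 30 | 38.5 | 22.1% | 50.0% |
| 488 | 29 | 32.5 | 10.8% | 51.7% |

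The 30% prompt never fires and no value is below 15. The central data show a fall of at least 50% from Day 366 to Day 488, that is 122 days. With no form there is no event, and if Day 488 is the last sample the patient is censored there. The prompt percentages depend only on the order of the values, so the same gap can arise over other runs of visits.

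Contrast an abrupt fall: 60 at Day 15, 48 at Day 29, 29 at Day 113. The prior mean is 54 and (54 − 29)/54 = 46.3%, so the prompt fires. The gap concerns gradual decline.

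**4. Size, under assumed completion rates.** If a proportion p of qualifying falls has no form, equally in both arms, events fall by p and the standard error of the log hazard ratio for these components is multiplied by 1/√(1 − p):
- p = 0.10: 1.05
- p = 0.20: 1.12
- p = 0.40: 1.29

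If completion differs by arm and events are uncommon, observed HR ≈ true HR × (completion on active / completion on placebo). With a true HR of 1.0:
- 80% active, 60% placebo: 0.80/0.60 = 1.33
- 60% active, 80% placebo: 0.60/0.80 = 0.75
- equal completion: 1.0

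**The case against.** The strongest case against has four parts.

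- **The definition is not settled.** The reference to the form may attach only to the no-repeat limb, and the laboratory-based censoring fits a laboratory-aware reading of the confirmed limb. This stands as a limit on the point. It also shows that the SAP should name the source for each limb.
- **Sites are prompted in several ways.** The 30% rule is more sensitive than a 50% threshold for abrupt falls. Protocol 6.1.2 adds an unscheduled visit for suspected renal events, and the visits from randomization on collect endpoint events with a pointer to the renal procedure. These reduce the risk. They do not remove it, because no stated prompt compares the value with baseline.
- **Little depends on the endpoint.** It is listed among the other endpoints, outside the fixed testing sequence in SAP 2.4.4.3. The ranked renal endpoint is the eGFR slope, which does not use the form. This stands.
- **Investigator reporting is disclosed and explained.** That is true, but incomplete adjudication is no reason against a programmed threshold on central values.

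A reader might infer three stronger things that the documents do not support. First, that local values enter through the form: the flow chart's laboratory footnote and Protocol 9.1.2.1 make post-randomization chemistry central, and nothing says the form takes local results. Second, that the censoring rule contradicts Appendix A's principle of censoring when last known event-free: under the form-based definition such a patient has no event, so the contradiction appears only once another definition is substituted. Third, that one arm's forms are more complete: Protocol 4.4.1 describes an acute, modest eGFR decrease on sotagliflozin, so a route exists, but the trial is double-blind and no quantity is given.

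**Conclusion.** The point holds with limits. On the most natural reading, events in the two eGFR components depend on a completed form while time at risk runs on laboratory dates. A gradual, sustained fall of at least 50% in the central data can then go unreported and be analysed as event-free. Whether the form also governs the confirmed limb is not clear from the table, and that needs resolving in any case.

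The number of patients affected cannot be derived. The precision losses of 5% to 29%, and the hazard ratios of 1.33 or 0.75 under a true null, rest entirely on assumed completion rates; equal completion leaves the hazard ratio about unchanged. The primary result, the ranked secondary endpoints and type I error are untouched. The change is worth making because it is cheap and replaces a dependence on site vigilance with data already held.

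**What to change.** Before unblinding, amend the renal definition table in SAP 2.1.3.3:

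- Derive the confirmed limb of both eGFR components by program from the central-laboratory series. Use the central randomization value as baseline, require the first qualifying value to be confirmed by a central value at least 30 days later, and date the event at the first qualifying sample.
- Keep chronic dialysis and renal transplant from the eCRF.
- Prespecify two sensitivity analyses: one adding falls with no later sample (the no-repeat limb), and one using the form-based definition.
- Tabulate form-versus-laboratory discordance by arm.

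The cost is SAP wording and one derived dataset, with no new samples. The downside is that late unconfirmed falls and form-only events move to the sensitivity analyses. Because follow-up ended early, some late falls will have no later central sample, so the main event count may go down.

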**Endpoint definitions of renal events for renal endpoint analysis**

Event	Endpoint definition
Sustained <math>\geq 50\%</math> decrease in eGFR from baseline	Confirmed <math>\geq 50\%</math> decrease in eGFR for <math>\geq 30</math> days OR with no repeat eGFR <math>\geq 30</math> days as recorded in eCRF “eGFR decrease”
Sustained eGFR $< 15$ mL/min/1.73 m 	Confirmed eGFR $< 15$ mL/min/1.73 m  for $\geq 30$ days OR with no repeat eGFR $\geq 30$ days as recorded in eCRF “eGFR decrease”
Chronic dialysis	Dialysis lasted for $\geq 90$ days (e.g. end date – start date+ 1 $\geq 90$ ) as recorded in eCRF “Renal Event – Dialysis”, or answered Yes to the question “Does the subject meet the criteria for ESRD”.
Renal transplant Reference source not found.	“Renal transplant” captured in eCRF “Other procedure form”. PTs of Renal transplant, Renal and pancreas transplant, Renal and liver transplant based on MedDRA v23.0.

**2.1.4 Safety endpoints**

The period of safety observation starts from the time when the patient gives informed consent and is divided into three periods:

- Pre-treatment period: defined from the signed informed consent up to the first dose of double-blind IMP.
- Treatment-emergent adverse event (TEAE) period: defined as the time from the first dose of double-blind IMP injection to the last dose of double-blind IMP dose +10 days.
- Post-treatment period: defined as the time starting the day after the end of the TEAE period.

**2.1.4.1 Adverse events variables**

Occurrence of AEs (including serious adverse events [SAEs], and AEs of special interest [AESIs]) are recorded from the time of signed informed consent until the end of study.

All AEs will be coded to a Lowest Level Term (LLT), PT, High Level Term (HLT), High Level Group Term (HLGT), and associated primary System Organ Class (SOC) using the version of MedDRA currently in effect at the time of the database lock.

Adverse event observation periods:

- Pre-treatment AEs are AEs that developed or worsened or became serious during the pre-treatment period;
- Treatment-emergent AEs are adverse events that developed or worsened or became serious during the TEAE period;
- Post-treatment AEs are AEs that developed or worsened or became serious during the post-treatment period.

***Adverse Events of Special Interest***

- Pregnancy of a female patient entered in a study as well as pregnancy occurring in a female partner of a male patient entered in a study with IMP
- Symptomatic overdose (serious or nonserious) with IMP
- ALT  $\geq 3$  x ULN (if Baseline ALT < ULN) or ALT  $\geq 2$  times the Baseline value (if Baseline ALT  $\geq$  ULN)

***Events of Special Interest :***

- Venous thrombotic events to include deep venous thrombosis and thromboembolism (to include pulmonary embolism)
- Pancreatitis
- Bone fractures
- Adverse events leading to amputation(s)
- Diabetic ketoacidosis
- Malignancies of special interest (breast, bladder, renal cell, Leydig cell, pancreatic, prostate, and thyroid follicular cell carcinoma)
- Genital mycotic infections (to include vulvovaginal candidiasis in females and candida balanitis in males)
- Urinary tract infections
- Diarrhea
- Clinically relevant volume depletion and events related/possibly related to volume depletion
- Severe hypoglycemia
- Fournier's gangrene

EOSI will be identified based on criteria in the table below. Of note, drug-induced liver injury is not listed as an EOSI, but it will be described in the same manner, with a presentation of the number and percentage of events in each treatment group.

Identification criteria for EOSI	
AE Grouping	Criteria
Bone Fractures	Investigator's opinion: eCRF form "Adverse Events" and its associated complementary form "Bone Fracture";
Diabetic ketoacidosis	Investigator's opinion: eCRF form "Adverse Events" and its associated complementary form "METABOLIC ACIDOSIS/SUSPECTED DKA"
Venous thrombotic events	Identified by using MedDRA preferred terms listed in Appendix D
Pancreatitis	Identified by using MedDRA preferred terms listed in Appendix D
Malignancies of special interest (breast, etc)	Breast cancer: Narrow search on "Breast neoplasms, malignant and unspecified (SMQ)" [20000149]  Prostate cancer: Narrow search on "Prostate neoplasms, malignant and unspecified (SMQ)" [20000152]  Leydig-cell cancer: PTs in Appendix D  Thyroid cancer: PTs in Appendix D  Renal cell cancer: PTs in Appendix D  Pancreatic cancer: PTs in Appendix D  Bladder cancer: PTs in Appendix D
Genital mycotic infections	Identified by using MedDRA preferred terms listed in Appendix D
Urinary tract infection	Identified by using MedDRA preferred terms listed in Appendix D
Diarrhea	Narrow search on "Noninfectious diarrhoea (SMQ)" [20000218] plus the following PTs (MedDRA v21.1): Gastroenteritis (10017888), Antidiarrhoeal supportive care (10055660), Enteritis (10014866), Enteritis leukopenic (10014877), Enterocolitis (10014893), Enterocolitis haemorrhagic (10014896)
Volume depletion	Identified by using MedDRA preferred terms listed in Appendix D
Severe hypoglycemia	Finish eCRF form "Hypoglycemia event information" and meet the criteria:  To the question "Assistance Required", ticked the option "Required assistance because subject was not capable of helping self", and  To the question "Were Symptoms Present", ticked "Yes".
EOSI AE related with amputation (non-traumatic)	
Amputation (non-traumatic)	Identified on the eCRF 'Other procedures related to Amputation'
AE leading to amputation (non-traumatic)	'AE correction' as the reason for amputation in eCRF 'Other procedures related to Amputation'
Potential cases of Fournier's Gangrene	
Potential cases of Fournier's gangrene a	Identified by using MedDRA preferred terms listed in Appendix D

\*Search terms will be updated using the MedDRA version currently in effect at Sanofi at the time of database lock for EOSI identified for them.

a Potential cases of Fournier's gangrene: not an EOSI per protocol; analyzed due to a warning released by health authorities in 3Q 2018 about rare occurrences of a serious infection of the genital area with FDA-approved SGLT2 inhibitors for diabetes.

